12.3.3.1 Analysis of Primary Efficacy Variables

The primary efficacy endpoint is the change from baseline in UEMS at 6 months after treatment. The null hypothesis to be tested is that the mean change from baseline in UEMS at 6 months after treatment is the same for 9-mg dose of VX-210 and placebo.

The primary analysis will be based on a mixed-effects model for repeated measures (MMRM). The model will include the change from baseline in UEMS as the dependent variable; treatment, visit, and treatment-by-visit interaction as fixed effects; and subject as a

random effect, with adjustment for age and AIS grade (A versus B with sacral pinprick preservation versus B without sacral pinprick preservation) at baseline. In the model, visit will be treated as a class variable, and an unstructured covariance matrix will be assumed to model the within-subject variability. This model imposes no assumptions on the correlation structure and is considered robust. Denominator degrees of freedom for the F-test for fixed effects will be estimated using the Kenward-Roger approximation.⁵² With a mixed-effects model based on restricted maximum likelihood estimation as the primary analysis and assuming that, conditional on fixed and random effects, data are missing at random, no imputation of missing data will be performed.

The primary result obtained from the model will be the estimated mean treatment effect at 6 months after treatment. The estimated mean treatment effect, a 95% CI, and a 2-sided *P* value will be provided. Furthermore, the treatment effect at each postbaseline visit, obtained from the model, will also be provided.

If there is a convergence problem due to the use of an unstructured covariance matrix, the unstructured covariance matrix will be replaced by a compound symmetric covariance matrix to model the within-subject errors.

12.3.3.2 Analysis of Secondary Efficacy Variables

For all secondary efficacy variables, the primary analysis will focus on the treatment effects at 6 months after treatment.

- SCIM III Self-Care subscore at 6 months after treatment: The analysis of this variable will be based on an analysis of covariance (ANCOVA) model, which will include the SCIM III Self-Care subscore at 6 months after treatment as the dependent variable, and treatment as a fixed effect, with adjustment for age and AIS grade (A versus B with sacral pinprick preservation versus B without sacral pinprick preservation) at baseline. If the SCIM III Self-Care subscore at 6 months after treatment is missing, the score at the Early Termination Visit will be carried forward for the analysis.
- CUE-T score at 6 months after treatment: The analysis of this variable will be similar to the analysis of the SCIM III Self-Care subscore.
- GRASSP Quantitative Prehension score at 6 months after treatment: The analysis of this variable will be similar to the analysis of the SCIM III Self-Care subscore.
- AIS grade conversion from baseline to 6 months after treatment: The response variable will be analyzed using the 2-sided Cochran-Mantel-Haenszel (CMH) test stratified by age (<30 versus ≥30 years of age) and AIS grade (A versus B with sacral pinprick preservation versus B without sacral pinprick preservation).
- Motor level change from baseline to 6 months after treatment: The analysis of this response variable will be similar to the analysis of the AIS grade conversion from baseline to 6 months after treatment.

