12.1 Sample Size and Power

The primary efficacy endpoint is the change from baseline in UEMS at 6 months after treatment.

The null hypothesis to be tested is that the mean change from baseline in UEMS at 6 months after treatment is the same for 9-mg dose of VX-210 and placebo. This null hypothesis will be tested at 2-sided significance level $\alpha = 0.05$.

The sample size was calculated using a projected standard deviation (SD) of 6.0, based on the variability of improvement in UEMS scores of cervical subjects in the historical Sygen database. Anticipated withdrawal of 10% of subjects before the first follow-up assessment was also included in the sample size calculation.

If 9-mg dose group improves in UEMS by 4 points over placebo (a clinically meaningful increase), a total of approximately 100 subjects (approximately 50 per arm) will have

approximately 82.1% power to detect a statistically significant treatment effect for 9-mg dose group compared to placebo, considering the interim futility analysis.

Based on the review of data from Anderson et al.,³⁸ the SD was projected to be 3.8 for SCIM III Self-Care subscore. Table 12-1 presents the estimated power for detecting different treatment differences between an active treatment group and the placebo group in SCIM III Self-Care subscore, assuming 45 randomized subjects with follow-up assessment in each treatment group without considering the possible power loss from the interim futility analysis.

Table 12-1 Power Estimates Under a Variety of Treatment Differences, Given 45 Randomized Subjects With Follow-up Assessments in Each Treatment Group

Mean Difference in SCIM III Self-Care Subscore	Power (%)
1	23
2	69
3	95

Power estimates are based on 2-sided t-test with $\alpha = 0.05$.

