9.3.2 Analysis of Secondary Efficacy Variables

9.3.2.1 Secondary Analyses

Secondary efficacy endpoints will be summarized using descriptive summary statistics by treatment group and all post-baseline follow-up visits (AIS grade and motor level will also be summarized descriptively at baseline).

- SCIM III Self-Care subscore at 6 months after treatment: The range of the SCIM III Self-Care subscore is 0-20. The score collected in the CRF will be directly used in the analysis. The SCIM III Self-Care subscore at 6 weeks, 3 months, 6 months, and 12 months after treatment will be summarized descriptively by treatment group.
- CUE-T score at 6 months after treatment: The range of the CUE-T score is 0-128. The score collected in the CRF will be directly used in the analysis. The CUE-T score at 6 months after treatment will be summarized descriptively by treatment group.

- GRASSP Quantitative Prehension score at 6 months after treatment: The GRASSP Quantitative Prehension score will be derived as described in Appendix F. The range of the score is 0-60. The GRASSP Quantitative Prehension score at 6 months after treatment will be summarized descriptively by treatment group.
- AIS grade conversion from baseline at 6 months after treatment: An AIS responder is defined as a subject with improvement by ≥ 2 AIS grades (i.e., baseline AIS grade A changed to grade C, D, or E; baseline AIS grade B changed to D or E at 6 months after treatment). The AIS grade at baseline, 6 weeks, 3 months, 6 months, and 12 months after treatment will be summarized descriptively by treatment group. The AIS responder, defined as aforementioned, at 6 weeks, 3 months, 6 months, and 12 months after treatment will also be summarized descriptively by treatment group.

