10.1.2 Interim Efficacy Analysis

For the interim futility analysis data review meeting, the IDMC will be provided with statistical analyses of the following primary and secondary study endpoints and supportive data listings as appropriate. For all the interim efficacy analyses, no *P* value will be provided. All the efficacy endpoints aforementioned will be analyzed based on the FAS.

- Change from baseline in the UEMS score at 6 months after treatment: The UEMS score will be summarized at baseline, 6 weeks, 3 months, 6 months, and 12 months after treatment using the descriptive summary statistics by treatment group. The change from baseline in the UEMS score at 6 weeks, 3 months, 6 months, and 12 months after treatment will also be summarized descriptively by treatment group. The MMRM analysis of the change from baseline in the UEMS score at 6 months after

treatment in the interim analysis is similar to the MMRM analysis of the same variable in the primary analysis (see section 9.3.1.2) except for that no *P* value will be provided.

- **SCIM III Self-Care subscore at 6 months after treatment:** The SCIM III Self-Care subscore at 6 weeks, 3 months, 6 months, and 12 months after treatment will be summarized descriptively by treatment group. The analysis of the SCIM III self-care subscore at 6 months after treatment will be based on an ANCOVA model, which will include the SCIM III self-care subscore at 6 months after treatment as the dependent variable, and treatment as a fixed effect, with adjustment for age and AIS grade (only including A versus B with sacral pinprick preservation versus B without sacral pinprick preservation) at baseline. If the SCIM III self-care subscore at 6 months after treatment is missing after the visit windows rules have been applied, the score at the early termination visit will be carried forward for the analysis. The estimated mean treatment effect (LS means difference) at 6 months after treatment and a 95% CI will be provided. No *P* value will be provided.
- **CUE-T score at 6 months after treatment:** The CUE-T score at 6 months after treatment will be summarized descriptively by treatment group. The ANCOVA analysis of the CUE-T score at 6 months after treatment is similar to the ANCOVA analysis of the SCIM III Self-Care subscore at 6 months after treatment in the interim analysis except for that the relevant endpoint here is the CUE-T score at 6 months after treatment.

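### The protocol's month-6-only ANCOVA for SCIM III Self-Care drops subjects who have earlier scores but no month-6 or exit score; the cost is conditional and modest, and a repeated-measures model would avoid it

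*Protocol*

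**What the plan says.** **Protocol.** Section 12.3.3.2 specifies an ANCOVA for SCIM III Self-Care, "which will include the SCIM III Self-Care subscore at 6 months after treatment as the dependent variable", with a treatment effect and adjustment for age and AIS grade. A missing month-6 score is replaced by the Early Termination score; no other rule is given. Section 12.3.3.4 tests this endpoint at Step 2, after UEMS.

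Table 3-1 schedules SCIM III at 6 weeks and 3, 6 and 12 months, the same follow-up visits as the ISNCSCI examination that yields UEMS. Section 12.3.3.1 analyses UEMS by MMRM with unstructured covariance, assuming data missing at random and imputing nothing.

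**SAP.** For the final analysis, the visible text of Section 9.3.2.1 says only: "The SCIM III Self-Care subscore at 6 weeks, 3 months, 6 months, and 12 months after treatment will be summarized descriptively". Section 9.3.4 marks multiplicity adjustment as not applicable. The ANCOVA appears in Section 10.1.2, where the interim SCIM analysis "will be based on an ANCOVA model", with an estimate and 95% CI but no P value. Section 9.1 keeps the Early Termination carry-forward, applied after visit windowing. Parts of the SAP are redacted, so this describes what can be read.

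**The concern.** The first two endpoints in the protocol's hierarchy are measured at the same visits but treat missing data differently. Consider a dosed subject seen at 6 weeks and 3 months who then withdraws consent, dies or cannot be reached. If there is no exit examination, the UEMS model keeps that subject's observed scores, whereas the SCIM ANCOVA has no record to use.

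Two things are at stake. One is precision, because scores already on file are not used for such subjects. The other is bias. If the chance of being lost depends on function at month 3, and does so differently by arm, a complete-case comparison at month 6 is biased, while an MMRM that conditions on the earlier scores is not, provided that missing at random holds.

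**Working it through.** **Inputs from the documents (Protocol 12.1).** For the SD, "the SD was projected to be 3.8 for SCIM III Self-Care subscore". The sample size for the SCIM power table is stated as "assuming 45 randomized subjects with follow-up assessment in each treatment group". The test is a 2-sided t-test at 0.05. The only dropout allowance is 10% before the first follow-up assessment: 50 × 0.9 = 45 per arm.

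**Inputs not in the documents (assumed).**
- f: the share of the 45 per arm who have an earlier SCIM score but no month-6 and no exit score. Taken as 3% to 10%.
- R²: the share of month-6 variance explained by the earlier visits. Taken as 0.25 to 0.81 (correlation 0.5 to 0.9).

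**1. The plan's own table.** The noncentrality is Δ / (SD × √(2/n)) with 2n − 2 degrees of freedom. For n = 45 and SD 3.8 the standard error is 3.8 × √(2/45) = 0.801. Power at 1, 2 and 3 points is 23.5%, 69.5% and 95.9%, against 23%, 69% and 95% in Table 12-1. The table reproduces.

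**2. Complete month-6 data.** A simulated complete data set (45 per arm, three visits) was fitted both ways. The month-6 difference was 2.581 with SE 0.715 from the single-visit ANCOVA and from the repeated-measures fit. Leaving out the earlier visits costs nothing in this case.

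**3. The planned 10% withdrawal.** These subjects leave before any SCIM score exists, so an MMRM has nothing to recover from them.

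**4. Later loss without an exit score.** The ANCOVA uses 45(1 − f) per arm. Under missing at random the MMRM has an effective size of about 45 / [(1 − R²)/(1 − f) + R²]. For example, with f = 0.10 and R² = 0.81, 0.19/0.90 + 0.81 = 1.021 and 45/1.021 = 44.1. The formula treats the correlation as known, so it slightly flatters the MMRM.

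Power at a 2-point difference, SD 3.8:

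| f | ANCOVA n per arm | ANCOVA power | MMRM effective n (R² 0.25 to 0.81) | MMRM power |
|---|---|---|---|---|
| 0 | 45 | 69.5% | 45 | 69.5% |
| 3% | 43.7 | 68.1% | 44.0 to 44.7 | 68.5% to 69.2% |
| 5% | 42.8 | 67.2% | 43.3 to 44.6 | 67.8% to 69.0% |
| 10% | 40.5 | 64.8% | 41.5 to 44.1 | 65.9% to 68.5% |

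From these rounded figures, the gain is about 0.4 to 1.1 points at 3% and 1.1 to 3.7 points at 10%. At 10% the SE falls from 0.844 to between 0.834 and 0.810.

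**5. Bias of the complete-case comparison.** Suppose a share m of one arm is lost, those lost scored k SDs below their arm's mean at month 3, the month-3 to month-6 correlation is ρ, and loss in the other arm is random. The bias is then m/(1 − m) × ρ × k × SD.
- Upper-end case (m = 0.10, ρ = 0.8, k = 1): 0.111 × 0.8 × 1 × 3.8 = 0.34 points, or 17% of a 2-point effect.
- Mild case (m = 0.05, ρ = 0.5, k = 0.5): 0.0526 × 0.5 × 0.5 × 3.8 = 0.05 points.

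**The case against.** The strongest reply is that the affected group may be very small. SCIM III is scheduled at the Early Termination visit, withdrawing subjects are asked to attend it, withdrawn subjects continue to be followed unless they withdraw consent (Protocol 9.4), transport is offered, and the SAP's month-6 window runs from Day 137 to Day 273. No passage supports a further 10% loss. Added to the planned withdrawal, it would leave 40.5 of 50 per arm, or 19% without a usable month-6 score. This stands as a limit on size. It does not empty the group: after withdrawal of consent no further evaluations are made, and the exit visit for non-returners is only a request.

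Three stronger readings are tempting, and the documents support none of them.
- *A reader might infer that ignoring the earlier visits loses precision in itself.* It does not: with complete month-6 data the two analyses agree.
- *A reader might infer that the SCIM result will be biased.* The documents give no reason to expect different loss by arm in a blinded, single-dose trial. The 0.34 points comes from one chosen scenario.
- *A reader might infer that the final analysis will run Steps 1 and 2 on different subjects.* That describes the protocol. The visible SAP shows neither a final SCIM model nor a hierarchy.

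ANCOVA is also the common model for SCIM, CUE-T and GRASSP, so the change would separate SCIM from the other two. That is true, but CUE-T and GRASSP have only one routine follow-up visit, at month 6, and so have no 6-week or 3-month scores to use. The interim ANCOVA is of little consequence: the futility guideline uses UEMS only, and the SAP states that the interim methods have been carried out.

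**Conclusion.** The point holds in a limited form. The protocol's SCIM analysis excludes subjects who have earlier scores but no month-6 or exit score, and so departs from the missing-data approach used for UEMS at the same visits. The power cost is nil with complete month-6 data and nil for the planned early withdrawals. For an assumed 3% to 10% later loss it is about 0.4 to 3.7 points at a 2-point difference. The possible bias runs from negligible to about a third of a point and needs informative loss that differs by arm. Both ranges rest on values of f, R², ρ and k that the documents do not give. The change is worth making because it is cheap and aligns the first two steps of the protocol's hierarchy, not because the trial's conclusion is likely to turn on it.

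**What to change.** In Protocol 12.3.3.2, analyse SCIM III Self-Care with the UEMS model: the same visits (the SAP's UEMS model uses 6 weeks and 3, 6 and 12 months), treatment, visit and treatment-by-visit, the same age and AIS adjustment, unstructured covariance, Kenward-Roger degrees of freedom and the same convergence fallback. The dependent variable is the score itself, since SCIM III is not scheduled at screening. The 6-month contrast is the reported result and the Step 2 test.

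Enter each Early Termination score in the visit window in which it was taken, instead of carrying it forward to month 6. SAP Appendix B already gives ISNCSCI and SCIM III the same windows. Keep the ANCOVA with carry-forward as a sensitivity analysis.

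Reconcile SAP 9.1 (carry-forward), 9.3.2.1 (no visible final SCIM model) and 9.3.4 (no visible hierarchy) with the protocol. For the SAP this is more than swapping models: on its visible text, it means stating an inferential SCIM analysis and its place in the hierarchy, or else changing the protocol to say that none is intended.

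The cost is wording in both documents and reuse of the UEMS program, with no new data. The downside is one more covariance model that must converge.

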- **AIS C; Motor Incomplete:** Motor function is preserved at the most caudal sacral segments for voluntary anal contraction OR the patient meets the criteria for sensory incomplete status (sensory function preserved at the most caudal sacral segments (S4 to S5) by light touch, pin prick, or deep anal pressure) and has some sparing of motor function more than 3 levels below the ipsilateral motor level on either side of the body (This includes key or non-key muscle functions to determine motor incomplete status). For AIS C – less than half of key muscle functions below the single neurological level of injury have a muscle grade ≥ 3 .
- **AIS D; Motor Incomplete:** Motor incomplete status as defined above, with at least half (half or more) of key muscle functions below the single neurological level of injury having a muscle grade ≥ 3 .
- **AIS E; Normal:** If sensation and motor function as tested with the ISNCSCI are graded as normal in all segments, and the patient has prior deficits, then the AIS grade is E. Someone without an SCI does not receive an AIS grade.

Using “Not Determined” (ND): To document the ASIA Impairment Scale grade when it is unable to be determined based on the examination results.

Conversion of 2 or more AIS grades has been used previously as a clinical assessment of significant neurologic recovery.^{47,48}

The motor level for the right or left side is defined by the lowest key muscle function that has a grade of at least 3 (on supine testing), provided the key muscle functions represented by

segments above that level are judged to be intact (graded as a 5). Note: In regions where there is no myotome to test, the motor level is presumed to be the same as the sensory level, if testable motor function above that level is also normal. The motor level is determined for both the right and left sides of the body; the right and left motor level may be different. For additional details, please see the ISNCSCI Scoresheet in Section 15.1. An improvement of 2 or more motor levels on either side has been shown to correlate with functional improvements.^{4,30}

[figure not shown]

Table 8-1 Summary of Efficacy Endpoints and Assessments

Efficacy Endpoint	Efficacy Assessment
Primary Endpoint	
Change from baseline in upper extremity motor score (UEMS) at 6 months after treatment	ISNCSCI examination
Secondary Endpoints	
Spinal Cord Independence Measure (SCIM) III Self-Care subscore at 6 months after treatment	SCIM III

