9.1 Inclusion Criteria

Subjects who meet all of the following inclusion criteria will be eligible.

1. Subject (or a witness, or his or her legally appointed and authorized representative) will sign and date an informed consent form (ICF).
2. Willing and able to comply with scheduled visits, treatment plan, laboratory tests, contraceptive guidelines, and other study procedures.
3. Subjects are male or female between 14 and 75 years of age, inclusive.
4. Acute traumatic cervical SCI, motor level of C4, C5, C6, or C7 on each side:
 - Screening UEMS score must be ≤ 16 points on each side.
 - AIS A subjects with a C4 motor level on both sides must have at least 1 point of motor activity between C5 and T1 on at least 1 side.
 - AIS B subjects with a C4 motor level on both sides must have at least 1 point of motor activity between C5 and C7 on at least 1 side.
5. AIS grade A or AIS grade B.
6. Scheduled and planned to undergo a spinal decompression/stabilization surgery that commences within 72 hours after the initial injury.
7. Computed tomography (CT) scan or magnetic resonance imaging (MRI) is consistent with the subject's neurological deficit.

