11.5.1 ISNCSCI Examination

The ISNCSCI examination will be conducted at time points indicated in [Table 3-1](#) and will be conducted by an independent, trained assessor. All efforts will be made to use the same assessor for all ISNCSCI examinations for a given subject. All trained assessors must meet Vertex requirements provided in the Assessment Handbook and must complete required training.

In addition to providing detailed motor and sensory scores, this assessment will determine the right and left motor levels, AIS Grade, neurological level, and complete/incomplete status.

Specifics on proper ISNCSCI administration will be provided in the Assessment Handbook.

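### The protocol's ANCOVAs of SCIM III Self-Care, CUE-T and GRASSP adjust for age and AIS grade but for no measure of baseline arm impairment; the comparison is valid but loses precision.

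*Protocol*

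**What the plan says.** **Model.** Protocol 12.3.3.2 analyses the 6-month SCIM III Self-Care subscore by ANCOVA: the score enters "as the dependent variable, and treatment as a fixed effect, with adjustment for age and AIS grade", the grade having three levels. For CUE-T, and in the same words for GRASSP, "The analysis of this variable will be similar to the analysis of the SCIM III Self-Care subscore". The interim ANCOVAs in SAP 10.1.2 use the same covariates, "with adjustment for age and AIS grade (only including A versus B with sacral pinprick preservation versus B without sacral pinprick preservation) at baseline".

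**No own baseline.** The schedule (protocol Table 3-1, SAP Table 12-1) has no SCIM III, CUE-T or GRASSP at screening. Only the ISNCSCI examination is done before dosing.

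**Arm impairment is recorded.** Entry requires "Acute traumatic cervical SCI, motor level of C4, C5, C6, or C7 on each side" (protocol 9.1). Of the ISNCSCI, protocol 11.5.1 says "this assessment will determine the right and left motor levels, AIS Grade, neurological level, and complete/incomplete status". Exclusion criterion 3 in protocol 9.2 removes anyone with an untestable arm muscle group at screening, so UEMS should be complete at baseline. SAP 9.2.2 already tabulates baseline UEMS (total, left, right), and SAP 9.3.2.1 adds that "AIS grade and motor level will also be summarized descriptively at baseline". Randomisation is stratified by age and AIS grade, not by level or arm strength (protocol 10.3).

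**Final analysis in the SAP.** SAP 9.3.2.1 says "Secondary efficacy endpoints will be summarized using descriptive summary statistics by treatment group and all post-baseline follow-up visits". No ANCOVA of these scores is visible there, and SAP 9.3.4 marks multiplicity as not applicable, whereas protocol 12.3.3.4 makes SCIM III Self-Care the second step of a testing hierarchy.

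**The concern.** AIS grades A and B describe completeness of the injury, judged by sacral sparing. They do not say how much of the arm works. Two subjects of the same age and grade can therefore enter with very different arm strength, and the model treats them as exchangeable. Self-Care depends on hand and arm control (protocol 8.2.3.2), and CUE-T and GRASSP test arm and hand tasks directly, so starting strength is a natural source of variation in the 6-month scores. With no pre-dose score on these instruments, motor level and UEMS are the obvious baseline measures to absorb it.

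At stake is precision on the functional endpoints, above all SCIM III Self-Care. Under protocol 12.3.3.4 it gates the later functional tests, and its tabulated power is 69% for a 2-point difference.

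**Working it through.** **1. Range of arm strength within one AIS grade.** UEMS grades 5 muscle groups per side from 0 to 5, total 50 (protocol 8.2.3.1). Protocol 9.1 caps each side at 16, so the maximum at entry is 2 × 16 = 32. A subject with C4 on both sides may enter with a single point. By the motor-level definition in protocol 8.2.3.2, C7 on a side needs C5 and C6 at 5 and C7 at 3 or more: at least 5 + 5 + 3 = 13 points, or 26 if bilateral. Strength at entry can thus run from 1 to 32 points within one grade.

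**2. Reproducing the plan's power.** Inputs from protocol 12.1: SD 3.8, 45 per arm, two-sided t-test, alpha 0.05.

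- SE of the difference = 3.8 × √(2/45) = 0.801
- Noncentrality at 2 points = 2 / 0.801 = 2.50, with 88 df and critical value 1.987
- Noncentral-t power at 1, 2 and 3 points = 23.5%, 69.5%, 95.9%; protocol Table 12-1 gives 23%, 69%, 95%

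The table reproduces as an unadjusted comparison.

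**3. Adding one baseline arm covariate.** The documents give no R-squared. Let R² be the further share of variance explained, and take 3.8 as the SD before the covariate is added. Then residual SD = 3.8 × √(1 − R²), 95% CI half-width = t × residual SD × √(2/45), and the equivalent total N = 90 / (1 − R²). One degree of freedom is charged (87 df).

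| R² (assumed) | Residual SD | Power at 2 points | CI half-width (points) | Equivalent N |
|---|---|---|---|---|
| 0 | 3.80 | 69% | 1.59 | 90 |
| 0.05 | 3.70 | 72% | 1.55 | 95 |
| 0.10 | 3.60 | 74% | 1.51 | 100 |
| 0.20 | 3.40 | 79% | 1.42 | 112 |
| 0.30 | 3.18 | 84% | 1.33 | 129 |

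**4. Sensitivity to the starting SD.** The 3.8 enters a test without covariates, so the planned ANCOVA may already do better than 69%. If age and AIS grade explained 20% (assumed), the SD would start at 3.8 × √0.8 = 3.40 and power at about 79%. A covariate explaining a further 10%, 20% or 30% of what remains would give about 83%, 87% or 91%.

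**5. If the covariate explained nothing.** Moving from 88 to 87 df changes power at 2 points by about 0.01 percentage point. Chance imbalance adds about 1/(90 − 4) = 1.2% to the variance on average, which takes power from 69.5% to about 69.0%.

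**The case against.** **Little live target in the SAP.** The only visible SAP ANCOVAs of these scores are the interim ones, and SAP section 4 says the interim methods have been carried out. The visible final analysis is descriptive, without a hierarchy. This stands: the point applies to protocol 12.3.3.2 and to any final ANCOVA run under it, not to the completed interim analysis. SAP section 9.3.3 is absent from the public copy, so further models cannot be excluded.

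**The cited link concerns change.** Protocol 8.2.3.2 says "An improvement of 2 or more motor levels on either side has been shown to correlate with functional improvements", and protocol 8.2.3.1 likewise relates UEMS recovery to functional improvement. A reader might infer that the protocol itself shows baseline level to predict the 6-month score; it does not. The case rests on what the instruments measure and on the spread of strength allowed at entry.

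**The size is assumed.** This stands. The entry limits (C4 to C7, at most 16 points per side) also restrict what the covariate can explain, and at R² = 0.05 the gain is only 2 to 3 points of power. Nor do the documents name 2 points as the SCIM target; at 3 points the tabulated power is already 95%.

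**Adjusting for the randomisation factors is coherent.** It is, and type I error is controlled. A reader might infer that chance imbalance in injury level biases the functional comparison. It does not: under randomisation the test and interval already allow for such imbalance, at the price of a wider interval.

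**The primary endpoint is not a clean contrast.** A reader might infer that its change score disposes of baseline strength. It subtracts baseline with a slope of 1, and change can still depend on baseline.

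**Conclusion.** The concern holds as one of efficiency. The protocol's ANCOVAs of the three functional scores give valid inference but leave out a plausible prognostic measure that is available for every subject, where the outcome's own baseline is not.

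For SCIM III Self-Care at 2 points the gain runs from 69% to about 72%, 74%, 79% or 84% for a further 5%, 10%, 20% or 30% of variance explained. This rests on an assumed R², on 3.8 being the SD before the covariate is added, and on 45 per arm. If age and AIS grade already lower that SD, both the start and the end of the range are higher. The documents allow no comparable figures for CUE-T or GRASSP, since they give no SD for either.

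The stronger readings, that the comparison is biased or that 69% is the power of the planned ANCOVA, are not supported.

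**What to change.** In protocol 12.3.3.2, pre-specify one baseline arm-impairment covariate from the last pre-dose ISNCSCI for the SCIM III Self-Care, CUE-T and GRASSP models. Either of two forms will do, each using 1 degree of freedom:

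- baseline total UEMS, which is the finer scale; or
- the mean of right and left motor level, coded C4 = 4 to C7 = 7, which treats the levels as equally spaced.

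Choose one, and state it before final database lock and unblinding, as SAP section 4 requires of SAP revisions.

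Reconcile the two documents on whether a final ANCOVA of these endpoints will be run at all. If so, state the model with this covariate in SAP 9.3.2.1. If only descriptive summaries are intended, the protocol text should say so. The completed interim ANCOVAs need no change.

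The cost is 1 degree of freedom and a wording change in the protocol as well as the SAP. No new data, visit or procedure is needed.
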